3.4. Baseline Variables

Demographic and baseline characteristics include:

- Age.
- Sex.
- Ethnicity.
- Race.
- Duration of disease.
- Lean body mass (%) measured by DEXA and BIA.
- Body fat (%) measured by DEXA and BIA.
- Adipose tissue distribution measured by abdominal CT.
- IGF-1 SDS.
- BMI.
- Waist circumference.
- Vital Signs.
- Height, Height SDS, and Weight.

Height SDS will be determined from the age and gender standards listed in the national survey in year 2000² [based on data of the Ministry of Health, Labor and Welfare's Infant and Children's Growth Survey Report (0 to 6 years old) and the Ministry of Education, Culture, Sports, Science and Health Statistics Report (6 to 17 years old)].

3.5. Safety Endpoints

3.5.1. Adverse Events

Treatment-Emergent Adverse events (TEAEs) and Serious Adverse Events (SAEs) will be assessed.

3.5.2. Laboratory Data

The following safety laboratory tests will be collected.

Table 2. Protocol-Required Safety Laboratory Assessments

Hematology	Chemistry	Endocrinology
WBC count	General condition Total protein	Pregnancy test β -hCG ^a
Hemoglobin	Albumin	
Hematocrit		
RBC count		Growth hormone
MCV	Lipid Total cholesterol	IGF-1
MCH	Triglyceride	
MCHC	HDL cholesterol	Adrenal glands function
Platelet count	LDL cholesterol	Cortisol
	Liver function AST	Thyroid function
	ALT	TSH
	ALP	FT4
	Total bilirubin	
	Renal function BUN	Gonadal function
	Creatinine	LH
	Electrolyte Calcium	FSH
	Sodium	E2
	Potassium	Testosterone
	Chloride	
	Glucose metabolism HbA1c	
	Casual blood glucose ^b	

- a. Both local serum and urine testing will be acceptable. A urine pregnancy test should have sensitivity of at least 25 mIU/mL. A serum hCG testing can be selected as an alternative to a serum β -hCG when clinically appropriate at the discretion of the investigator.
- b. For participants with preexisting diabetes.

3.5.3. Other Safety Endpoints

- Vital Signs

Vital signs will include temperature, systolic and diastolic blood pressure, and pulse rate.

- Bone Age

Bone age will be assessed only in pediatric participants by an X-ray picture of the left hand and wrist. If the participant reaches bone age of 17 for boys and 15 for girls, the assessment is not necessary after that.

- Physical Examinations, including Behavioral and Mental Health Status

A physical examination will include, at a minimum, assessments of the cardiovascular, respiratory, gastrointestinal, and neurological systems. Assessments of the behavioral/mental health status will also be included.

- Height, Height SDS, and Weight

Height and weight will also be measured and recorded. Height SDS will be calculated.

4. ANALYSIS SETS (POPULATIONS FOR ANALYSIS)

For purposes of analysis, the following analysis sets are defined:

Participant Analysis Set	Description
Full Analysis Set (FAS)	All participants assigned to study intervention and who take at least one dose of study intervention.
Efficacy Evaluable Set	All participants assigned to study intervention and who take at least one dose of study intervention and have at least one efficacy evaluation.

Defined Analysis Set	Description
Adherence to protocol regimen	For participants who experience major deviation of diet/exercise or other major protocol deviation and/or discontinuation of treatment or study withdrawal, all data after the major deviation and discontinuation will not be considered.

5. GENERAL METHODOLOGY AND CONVENTIONS

The complete analyses will occur when all participants have completed the treatment period.

5.1. Hypotheses and Decision Rules

In this study, no formal hypothesis testing will be conducted.

The efficacy will be evaluated comprehensively based on individual data and summary statistics in each cohort for the primary, secondary, CCI In addition, it will be confirmed in adult cohort that the point estimate of the least squares (LS) mean of the primary endpoint is above 0.

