2.1. Study Rationale

The purpose of the study is to evaluate the efficacy and safety of somatropin in a cohort of Japanese participants with PWS.

This study is planned to support a supplemental new drug application in Japan in response to the official development request issued by Research and Development Division, Health Policy Bureau and Pharmaceutical Evaluation Division, Pharmaceutical Safety and Environmental Health Bureau, MHLW.

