2.2. Background

Somatropin is indicated for the long-term treatment of children with growth disturbance due to various conditions and replacement therapy in AGHD and marketed in more than 100 countries over 30 years.

GH replacement therapy is recommended for both pediatric and adult patients with PWS¹ and somatropin is approved for pediatric PWS regardless of stature in European countries and for adult PWS in New Zealand. In Japan GH replacement has been approved since 2002 for "short stature without epiphyseal closure associated with PWS", and is not approved for the use of improving body composition in pediatric patients and any use in adult patients with PWS.

A nation-wide patient advocacy group submitted a petition for somatropin for the indication "improvement of body composition in pediatric and adult PWS" and the requested indication was judged as a high medical need at the 39th MHLW Committee on Unapproved/Off-label used Drugs on 26 Aug 2019. Thereafter the official development request was issued to Pfizer Japan on **CCI** [REDACTED] by Research and Development Division, Health Policy Bureau and Pharmaceutical Evaluation Division, Pharmaceutical Safety and Environmental Health Bureau, MHLW.

The outline of the study was agreed upon with the Pharmaceuticals and Medical Devices Agency (PMDA) on **CCI** [REDACTED]

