9. STATISTICAL CONSIDERATIONS

Detailed methodology for summary and statistical analyses of the data collected in this study is outlined here and further detailed in a SAP, which will be maintained by the sponsor. The SAP may modify what is outlined in the protocol where appropriate; however, any major modifications of the primary endpoint definitions or their analyses will also be reflected in a protocol amendment.

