9.3.2. Primary Endpoint(s)/Estimand(s) Analysis

The primary endpoint for the study is change from baseline to Month 12 in lean body mass (%) measured by DEXA.

Data will be evaluated individually and descriptively for each cohort.

For adult cohort, the least squares (LS) mean and its 95% CI of change from baseline to Month 6 and 12 in lean body mass (%) measured by DEXA will be estimated based on a Mixed-effects Models for Repeated Measures (MMRM). The model will include fixed effects for visit as a categorical variable, and baseline lean body mass value (%) and interaction between baseline lean body mass value (%) and visit as a continuous variable.

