5.2.2. Analyses for Continuous Endpoints

Descriptive summary statistics (number, mean, standard deviation, median, minimum, and maximum) will be presented.

Least squares (LS) mean and its 95% CI of change from baseline will be estimated based on a Mixed-effect Model Repeated Measures (MMRM). Visit, baseline value, and baseline value-by-visit interaction are fixed effects in the model.

The restricted maximum likelihood (REML) estimation method will be used with an unstructured covariance matrix to describe the covariance matrix. The Kenward-Roger degrees of freedom will be used.

If there are convergence issues with the model, the default Newton-Raphson algorithm will be changed to the Fisher scoring algorithm in the initial value. In the case where there are still model convergence issues, the Toeplitz covariance matrix structures will be tried when repeated measures are 2-time points. When those are more than 2-time points, the following variance-covariance matrix structures will be tried in this particular order until convergence is obtained: Heterogeneous Toeplitz [TOEPH], Heterogeneous Autoregressive (1) [ARH(1)], Toeplitz [TOEP], Autoregressive (1) [AR(1)], and Compound Symmetry [CS].

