6.1.1.1. Main Analysis

- Estimand strategy: Hypothetical (section 2.1.1).
- Analysis set: Efficacy Evaluable Set (Adherence to protocol regimen) (section 4).
- Analysis methodology: In adult cohort, change from baseline will be analyzed using a MMRM including data from Month 6, and 12 with visit, baseline value, and baseline value-by-visit interaction as fixed effects. In GH naïve pediatric and GH treated pediatric cohort, observed value and change from baseline will be summarized descriptively (section 5.2.2).

- Intercurrent events and missing data: All data after an intercurrent event (major deviation of diet/exercise, discontinuation of treatment, discontinuation of study, etc.), if collected, will not be considered. No imputation will be made for missing data.
- In adult cohort, the LS mean and its 95% CI will be presented. In GH naïve pediatric and GH treated pediatric cohort, the descriptive summary statistics will be presented.

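### Does the adult check that the LS mean is above 0 let sampling error go unreported?

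*SAP*

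**What the plan says.** SAP 5.1 and protocol 9.1 state that no formal hypothesis test is made, and the protocol synopsis agrees. The basis for judging efficacy comes first: "The efficacy will be evaluated comprehensively based on individual data and summary statistics in each cohort". An additional item for adults follows: "it will be confirmed in adult cohort that the point estimate of the least squares (LS) mean of the primary endpoint is above 0". In both documents some text just before that item is blacked out.

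The interval is planned separately, in three places:
- Protocol 9.3.2 has the MMRM estimate "the least squares (LS) mean and its 95% CI of change from baseline to Month 6 and 12 in lean body mass".
- SAP 5.2.2 repeats this as the general method: "Least squares (LS) mean and its 95% CI of change from baseline will be estimated". It specifies REML, an unstructured covariance and Kenward-Roger degrees of freedom.
- SAP 6.1.1.1, for the primary endpoint: "In adult cohort, the LS mean and its 95% CI will be presented".

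No visible text says how the interval bears on the check, or what is to be written if the estimate is positive and the interval includes 0. The synopsis plans 20 adults. The readable text gives no SD, expected effect, power or dropout rate, and a block after protocol 9.4 is blacked out.

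**The concern.** The sentence stands under a SAP heading that mentions decision rules, it speaks of confirming something, and it is the only numeric efficacy criterion that can be read in either document. A check on the sign alone takes no account of sampling error, and 20 participants leave plenty of it. The protocol also says of its purpose: "This study is planned to support a supplemental new drug application in Japan". A small positive estimate with a wide interval would satisfy the sentence as written. A report could then lean on a confirmed check where the data do not exclude no mean change. Fixing the reading in advance has some appeal too, because the study is open label and the sponsor may review data while it runs (protocol 9.4, SAP 7.1).

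**Working it through.** **Inputs.** From the documents: 20 adults (synopsis), the check (estimate above 0) and a two-sided 95% CI. Assumed, because the readable text gives neither: the true mean change d, in units of the SD of the 12-month change; 16 evaluable adults as a lower case; and the correlation r between baseline and change, from 0 to −0.5. The plan shows no operating characteristic for the check, so there is no figure of its own to reproduce.

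**Step 1, the sign check.** With complete data and the LS mean taken at the sample mean baseline, the LS mean equals the sample mean change. Then P(estimate > 0) = Φ(d√n).
- d = 0: Φ(0) = 0.500 at any n.
- n = 20, d = 0.2: Φ(0.894) = 0.814.
- n = 20, d = 0.5: Φ(2.236) = 0.987.
- n = 20, d = 0.8: Φ(3.578) = 0.9998.

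**Step 2, the interval.** Ignoring baseline adjustment, the CI lies above 0 when the observed mean exceeds t(0.975, n−1)/√n SD. For n = 20 this is 2.093/4.472 = 0.468 SD; for n = 16 it is 2.131/4 = 0.533 SD. The noncentral t distribution gives P(CI above 0) at n = 20 as 0.025, 0.133, 0.564 and 0.924 for d = 0, 0.2, 0.5 and 0.8.

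**Step 3, baseline adjustment.** The adjusted Month 12 model was simulated with 200,000 trials per setting. The share of positive estimates whose CI includes 0 is 1 − P(CI above 0)/P(estimate > 0). For n = 20:

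| d | P(estimate > 0) | P(CI above 0), r = 0 | P(CI above 0), r = −0.5 | Share, r = 0 | Share, r = −0.5 |
|---|---|---|---|---|---|
| 0 | 0.500 | 0.024 | 0.042 | 95% | 92% |
| 0.2 | 0.814 | 0.132 | 0.194 | 84% | 76% |
| 0.5 | 0.987 | 0.564 | 0.665 | 43% | 33% |
| 0.8 | 0.9998 | 0.922 | 0.956 | 8% | 4% |

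For example, at d = 0.5 and r = 0: 1 − 0.564/0.987 = 0.43. With 16 evaluable adults the shares are 79–86% at 0.2 SD and 42–53% at 0.5 SD, and about 15% at 0.8 SD with r = 0 (1 − 0.848/0.999).

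**Step 4, what the figures mean.**
- The top row is close to automatic. With no true change, any sign check passes half the time and a 95% interval lies above 0 about 2.5% of the time, so the share is 1 − 0.025/0.5 = 95%. That is a property of sign checks, not of this plan. The 50% is not an error rate either, because no alpha is set.
- The other rows depend heavily on the assumed effect.
- Every trial counted in the last two columns is one in which the planned output shows an interval that includes 0. The uncertainty missing from the check is in the table that reports the estimate.

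**The case for a change.** The best case for a change is that presenting an interval differs from saying how it limits a conclusion. Confirmation is a strong word for a sign, the application raises the stakes, and a clarifying sentence needs no new data or analysis. Part of this stands: the visible text is silent on a positive estimate with a CI that includes 0, and a note that the check is directional and is read with its CI would do no harm if made in both documents together.

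It does not amount to a needed change:
- The thing confirmed is that an estimate is above 0. No readable passage says that this establishes efficacy, so a ban on that claim forbids something nobody has proposed.
- A report statement that switches on whether the CI includes 0 would work much like a two-sided 5% test in a study that excludes testing. It would also rest on an imperfect benchmark. The adjusted interval treats the sample mean baseline as fixed, so at r = −0.5 its coverage of the population mean is about 92% (1 − 2 × 0.042 = 0.916).
- As a real threshold, the interval would be met in only about 56–67% of trials at an assumed 0.5 SD with 20 adults, against 99% for the sign. Protocol 4.2 gives rarity as the reason for a single arm, and protocol 2.2 records: "The outline of the study was agreed upon with the Pharmaceuticals and Medical Devices Agency (PMDA". Whether that agreement covered this sentence cannot be seen. Protocol 9 adds that "any major modifications of the primary endpoint definitions or their analyses will also be reflected in a protocol amendment".
- Changing the SAP alone would break its present agreement with protocol 9.1.

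Neither wording would attribute the change to treatment. The design has no control arm, and the CI describes a change from baseline.

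**Conclusion.** No change follows. The observation is accurate: the check uses the sign alone and nothing readable connects it to the interval. But the plan followed as written gives no wrong result. The same LS mean, the same 95% CI and the same descriptive summaries are reported either way, and a statistician writing the report would read the estimate with its interval. What remains is a detail of interpretation.

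Its size depends on the unknown effect: the CI includes 0 in most positive results if the true change is near 0.2 SD, and in few if it is near 0.8 SD. These figures assume normally distributed changes, complete data and a Month 12 model that approximates the MMRM. The blacked-out text may hold a rationale for the criterion or for the 20 adults, so the silence noted here is only that of the readable text.

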5.2. General Methods

5.2.1. Analyses for Binary Endpoints

The number, percentage and 95% confidence interval (CI) will be presented.

5.2.2. Analyses for Continuous Endpoints

Descriptive summary statistics (number, mean, standard deviation, median, minimum, and maximum) will be presented.

Least squares (LS) mean and its 95% CI of change from baseline will be estimated based on a Mixed-effect Model Repeated Measures (MMRM). Visit, baseline value, and baseline value-by-visit interaction are fixed effects in the model.

The restricted maximum likelihood (REML) estimation method will be used with an unstructured covariance matrix to describe the covariance matrix. The Kenward-Roger degrees of freedom will be used.

If there are convergence issues with the model, the default Newton-Raphson algorithm will be changed to the Fisher scoring algorithm in the initial value. In the case where there are still model convergence issues, the Toeplitz covariance matrix structures will be tried when repeated measures are 2-time points. When those are more than 2-time points, the following variance-covariance matrix structures will be tried in this particular order until convergence is obtained: Heterogeneous Toeplitz [TOEPH], Heterogeneous Autoregressive (1) [ARH(1)], Toeplitz [TOEP], Autoregressive (1) [AR(1)], and Compound Symmetry [CS].

5.2.3. Analyses for Categorical Endpoints

The frequency and percentage for each category will be presented.

5.3. Methods to Manage Missing Data

No imputation will be made for missing data.

6. ANALYSES AND SUMMARIES

Unless otherwise specified, data will be summarized by each cohort.

For change from baseline endpoints, it would require that a participant have a baseline value and at least 1 post baseline value to be included in the analysis for that endpoint.

6.1. Primary Endpoint(s)

6.1.1. Lean body mass (%) measured by DEXA at Month 12

6.1.1.1. Main Analysis

- Estimand strategy: Hypothetical (section 2.1.1).
- Analysis set: Efficacy Evaluable Set (Adherence to protocol regimen) (section 4).
- Analysis methodology: In adult cohort, change from baseline will be analyzed using a MMRM including data from Month 6, and 12 with visit, baseline value, and baseline value-by-visit interaction as fixed effects. In GH naïve pediatric and GH treated pediatric cohort, observed value and change from baseline will be summarized descriptively (section 5.2.2).

- Intercurrent events and missing data: All data after an intercurrent event (major deviation of diet/exercise, discontinuation of treatment, discontinuation of study, etc.), if collected, will not be considered. No imputation will be made for missing data.
- In adult cohort, the LS mean and its 95% CI will be presented. In GH naïve pediatric and GH treated pediatric cohort, the descriptive summary statistics will be presented.

6.1.1.2. Sensitivity/Supplementary Analyses

In adult cohort, observed value and change from baseline will be summarized descriptively.

6.2. Secondary Endpoint(s)

6.2.1. Lean body mass (%) measured by BIA at Month 12 [KEY SECONDARY]

6.2.1.1. Main Analysis

- Estimand strategy: Hypothetical (section 2.1.2).
- Analysis set: Efficacy Evaluable Set (Adherence to protocol regimen) (section 4).
- Analysis methodology: In adult cohort, change from baseline will be analyzed using a MMRM including data from Month 1, 3, 6, 9, and 12 with visit, baseline value, and baseline value-by-visit interaction as fixed effects. In GH naïve pediatric and GH treated pediatric cohort, observed value and change from baseline will be summarized descriptively (section 5.2.2).
- Intercurrent events and missing data: All data after an intercurrent event (major deviation of diet/exercise, discontinuation of treatment, discontinuation of study, etc.), if collected, will not be considered. No imputation will be made for missing data.
- In adult cohort, the LS mean and its 95% CI will be presented. In GH naïve pediatric and GH treated pediatric cohort, the descriptive summary statistics will be presented.

6.2.1.2. Sensitivity/Supplementary Analysis

In adult cohort, observed value and change from baseline will be summarized descriptively.

6.2.2. Body fat (%) measured by DEXA at Month 12

6.2.2.1. Main Analysis

- Estimand strategy: Hypothetical (section 2.1.2).
- Analysis set: Efficacy Evaluable Set (Adherence to protocol regimen) (section 4).
- Analysis methodology: In adult cohort, change from baseline will be analyzed using a MMRM including data from Month 6, and 12 with visit, baseline value, and baseline value-by-visit interaction as fixed effects. In GH naïve pediatric and GH

treated pediatric cohort, observed value and change from baseline will be summarized descriptively (section 5.2.2).

- Intercurrent events and missing data: All data after an intercurrent event (major deviation of diet/exercise, discontinuation of treatment, discontinuation of study, etc.), if collected, will not be considered. No imputation will be made for missing data.
- In adult cohort, the LS mean and its 95% CI will be presented. In GH naïve pediatric and GH treated pediatric cohort, the descriptive summary statistics will be presented.

6.2.2.2. Sensitivity/Supplementary Analysis

In adult cohort, observed value and change from baseline will be summarized descriptively.

6.2.3. Adipose tissue distribution measured by abdominal CT at Month 12

- Estimand strategy: Hypothetical (section 2.1.2).
- Analysis set: Efficacy Evaluable Set (Adherence to protocol regimen) (section 4).
- Analysis methodology: Observed value and change from baseline will be summarized descriptively (section 5.2.2).
- Intercurrent events and missing data: All data after an intercurrent event (major deviation of diet/exercise, discontinuation of treatment, discontinuation of study, etc.), if collected, will not be considered. No imputation will be made for missing data.
- The descriptive summary statistics will be presented.

6.2.4. Lean body mass (%) measured by DEXA at Month 6 (adult cohort only)

[figure not shown]
[figure not shown]
6.2.4.1. Main Analysis

- Estimand strategy: Hypothetical (section 2.1.2).
- Analysis set: Efficacy Evaluable Set (Adherence to protocol regimen) (section 4).
- Analysis methodology: Change from baseline will be analyzed using a MMRM including data from Month 6, and 12 with visit, baseline value, and baseline value-by-visit interaction as fixed effects (section 5.2.2).
- Intercurrent events and missing data: All data after an intercurrent event (major deviation of diet/exercise, discontinuation of treatment, discontinuation of study, etc.), if collected, will not be considered. No imputation will be made for missing data.
- The LS mean and its 95% CI will be presented.

6.2.4.2. Sensitivity/Supplementary Analysis

Observed value and change from baseline will be summarized descriptively.

CCI

[figure not shown]
CCI

- 
- 
- 
- 
- 

CCI

- 
- 
- 
- 
- 
- 
- 
- 
- 
- 

- CCI

6.4. Subset Analyses

Not applicable

6.5. Baseline and Other Summaries and Analyses

6.5.1. Baseline Summaries

Demographics and baseline characteristics listed in section 3.4 will be summarized according to CDISC and Pfizer standards (CaPS) for FAS.

6.5.2. Study Conduct and Participant Disposition

Participants evaluation, disposition, discontinuation will be summarized according to CaPS.

6.5.3. Study Treatment Exposure

The number of dosing days and actual administered dosage will be summarized according to CaPS.

Medication error data will be reported in a list.

6.5.4. Concomitant Medications and Nondrug Treatments

Prior drug and non-drug treatment, concomitant drug and non-drug treatment will be summarized according to CaPS.

